9.3.4 Male Subjects

Male subjects must commit to not father a child or donate sperm from first dose until 3 months post-last dose.

Male subjects (with female partners of childbearing potential) must commit to consistent and correct use of at least two effective methods of birth control from the Medical Screening Visit until 30 days after the last administration of investigational product.

- Condom and diaphragm with spermicide (foam, cream, gel, sponge)
- Condom and cervical cap with spermicide (foam, cream, gel, sponge)
- Non-hormonal intrauterine device (IUD)

Female partner(s) of male volunteers also have the option to use the following highly effective hormonal method of contraception: implants, injectables, combined oral contraceptives, and IUDs.

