9.2 Inclusion Criteria for Study Volunteers

1. Male or non-pregnant female, between 18 to 65 years of age (inclusive) at Screening Visit.
2. Subjects must give their signed and dated written informed consent (in English) to participate prior to commencing any study-related activities and must be willing to comply with study procedures, study restrictions, study protocol, and return for the required assessments.
3. Female subjects of either non-childbearing potential or of child-bearing potential who commit to consistent and correct use of at least one highly effective or two effective forms of contraception starting at least 4 weeks prior to the Screening Visit and for at least 30 days post last dose of study drug.
4. Generally healthy subjects with mild controlled asthma for 2 years at Screening Visit according to the Global Initiative for Asthma (GINA 2020) criteria²³.
5. No concomitant asthma treatment, except inhaled SABA.
6. [REDACTED]
7. [REDACTED]
8. [REDACTED]
9. Currently a non-smoker; having not used tobacco products (i.e. cigarettes, cigars, pipe tobacco) within the past year, and having \leq 10 pack-years of historical use. Use of electronic cigarettes or other inhaled nicotine delivery products, smoking and/or inhalation of cannabis using a device (e.g. vaping) will not be allowed during the study.
10. Agree to limit caffeine and consumption of cruciferous vegetables and grilled meats. Agree to prohibit concomitant medications (strong CYP1A2, 2B6 and 3A4 inhibitors).
11. Body mass index (BMI) within the range 18.5-35.0 kg/m².
12. Male subjects who commit to not father a child or donate sperm from first dose until 3 months post-last dose.
13. Male subjects (with female partners of childbearing potential) who commit to consistent and correct use of at least two effective methods of birth control for the duration of the study and 30 days after the last dose of study drug.
14. AST, ALT, ALP, TSH, White Blood Count, hemoglobin, glucose, albumin, electrolytes, total proteins and total bilirubin within the normal range.
15. Acceptable lipase, amylase, GGT, CPK, total cholesterol, triglycerides, and eosinophils levels as determined by the Investigator in consultation with the medical monitor.

16. [REDACTED]
17. [REDACTED]
[REDACTED]
[REDACTED]

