9.3.3 Female Subjects of Childbearing Potential

A woman is considered of childbearing potential (WOCBP) if she is not postmenopausal, not congenitally sterile; not diagnosed as infertile (and not undergoing treatment to reverse infertility); or has not undergone successful surgical sterilization (such as tubal ligation, bilateral oophorectomy, or hysterectomy). A woman is considered of non-childbearing potential if she is postmenopausal (naturally postmenopausal [no menses] for at least 1 year), surgically sterile (tubal ligation, bilateral oophorectomy, or hysterectomy), congenital sterility, or diagnosed as infertile and not undergoing treatment to reverse infertility.

WOCBP must commit to consistent and correct use of at least one highly effective or two effective forms of contraception starting at least 4 weeks prior to the Medical Screening Visit and until 30 days after the last administration of investigational product, such as total abstinence, intrauterine device, a double-barrier method, oral, transdermal, injected or implanted non- or hormonal contraceptive.

Subjects on hormonal contraceptives must have been on the same hormonal contraceptive for at least one month before the Medical Screening Visit and continue throughout the duration of the study.

WOCBP will be instructed to contact the Investigator immediately if they suspect they might be pregnant.

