17.1.1 Pregnancy

Any female with a confirmed positive pregnancy result during study participation (from the time of signing the informed consent form until the end of the clinical trial) will be excluded from the clinical trial or immediately withdrawn from the clinical trial. Because of the possibility that the fetus/embryo could have been exposed to the study drug through the parent and for the subject safety, the subject will be followed until the end of the pregnancy (including spontaneous or voluntary termination).

If a subject becomes pregnant or suspects that they became pregnant during the clinical trial, or within 30 days after the study is complete, they must notify clinical site.

The pregnancy will be recorded on a Pregnancy form (provided by the clinical site or the Sponsor) and reported to the Sponsor and IRB. In the absence of a pregnancy form, an adverse event form can be used.

Attempts to contact the subject to inquire about the status and progression of the pregnancy will be made at intervals deemed appropriate (e.g., at least every three months) until an outcome of the pregnancy is known. This contact will be documented.

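### Men must not father a child until 3 months after last dose, but their required birth control stops at 30 days, and the visible text gives no duty to report or follow a partner's pregnancy.

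*Protocol*

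**What the plan says.** Two rules bind male subjects, and each appears three times: in the Study Summary (section 4), in section 9.2 and in section 9.3.4.

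- **The ban on conception.** Criterion 12 admits "Male subjects who commit to not father a child or donate sperm from first dose until 3 months post-last dose". Section 9.3.4 repeats it as a duty: "Male subjects must commit to not father a child or donate sperm from first dose until 3 months post-last dose".
- **The method rule.** Criterion 13, for men with partners of childbearing potential, requires "at least two effective methods of birth control for the duration of the study and 30 days after the last dose of study drug". Section 9.3.4 words it as "at least two effective methods of birth control from the Medical Screening Visit until 30 days after the last administration of investigational product".

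Pregnancy reporting is in section 17.1.1. Withdrawal and follow-up are triggered by a positive result in a female during her own participation. The reason given is "Because of the possibility that the fetus/embryo could have been exposed to the study drug through the parent". The duty to notify the site begins "If a subject becomes pregnant or suspects that they became pregnant during the clinical trial" and runs to 30 days after the study is complete. The case then goes on a Pregnancy form, is reported to the sponsor and IRB, and is followed by contacts about every three months until the outcome is known.

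For women, section 9.3.3 adds: "WOCBP will be instructed to contact the Investigator immediately if they suspect they might be pregnant". Section 9.3.4 has no matching line for men. The other visible mentions of pregnancy (unmasking in 10.3.2, withdrawal reasons in 17.2.3, consent elements in 20.2) also concern subjects. The SAP does not address partner pregnancy.

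**The concern.** The two male rules serve one purpose, to prevent conception while paternal exposure might matter, yet they stop at different times. A man told that two methods are required until 30 days after last dose can reasonably take that as leave to stop, although his promise not to father a child has about two months left to run.

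The reporting rules do not cover a failure of that promise. The partner is not a subject, and the man is not a subject who becomes pregnant, so neither has a stated duty to tell the site, and no outcome follow-up is planned. What is at stake is the safety of a partner and fetus, and the loss of rare human exposure information on an early-stage drug. No efficacy result and no planned safety analysis depends on it.

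**Working it through.** The plan states no figure for this gap, so there is none to reproduce. The check is a comparison of texts plus calendar arithmetic.

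**Inputs**
- Ban ends 3 months after last dose (9.2 criterion 12; 9.3.4).
- Required methods end 30 days after last dose (9.2 criterion 13; 9.3.4).
- Visit 4b is Day 25 (11.6) and Visit 5b is Day 47 (11.8). Dosing continues through both visit days.
- Each treatment period is 7 days at home, with up to 3 more (10.1).
- Mean half-life on multiple dosing is 3.07 to 6.20 h (6.5).
- Assumption: both rules count from the same last dose of study product, active or placebo.

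**1. Length of the gap.** Three calendar months, counted from every date in 2021 to 2024, last 89 to 92 days.
- Shortest: 89 − 30 = 59 days.
- Longest: 92 − 30 = 62 days.
- Share of the post-dose ban covered by required methods: 30/92 = 33% to 30/89 = 34%.

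**2. The gap by treatment sequence.** In sequence BA the last ADX-629 dose is also the last dose of any product, so required methods end 30 days after ADX-629. In sequence AB the last ADX-629 dose is on Day 25 and the last placebo dose on Day 47: 47 − 25 = 22 days apart, or 25 if period 2 runs 3 days longer. Required methods then end 22 + 30 = 52 to 25 + 30 = 55 days after ADX-629. The gap between the two rules stays at 59 to 62 days in both sequences, because both count from the same last dose.

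**3. Size of exposure.** Active dosing is 7 + 2 = 9 days, or 12 with the extra 3. Thirty days are 720 h, which is 720/6.20 = 116 to 720/3.07 = 235 half-lives. Section 6.4 reports no mutagenic or clastogenic potential.

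**4. Who is covered by which pregnancy provision**

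| Provision | Female subject | Male subject's partner |
|---|---|---|
| Instruction to contact the Investigator (9.3.3 / 9.3.4) | yes | no |
| Duty to notify the site (17.1.1) | yes | no |
| Pregnancy form, sponsor and IRB (17.1.1) | yes | not stated |
| Follow-up to outcome (17.1.1) | yes | not stated |
| Birth defect as a serious adverse event (17.2, 17.2.2) | yes, once known | possible, once known |

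During the study, a case that a man chose to mention could also be noted at an adverse event query (12.2.5) or as a deviation (20.4). Both depend on his raising it.

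**The case against.** The strongest reply is that the two male rules form a coherent two-tier design: a strict method rule for the period nearest dosing, inside a longer promise about outcome. That is right as far as it goes. A reader might infer that the protocol contradicts itself or permits conception after day 30. It does neither, since the promise binds every man for the full 3 months. What lapses is only the stated means of keeping it.

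Second, 30 days is generous for a drug with this half-life, it matches the female rule, and alignment could equally be reached by shortening the ban. This also has force. A reader might infer that 30 days of contraception is unsafe; nothing in the documents shows that. But the sponsor chose 3 months, and the visible nonclinical text (6.3, 6.4) describes no reproductive toxicity study that would justify a shorter ban. Unless the sponsor gives a reason to shorten it, the method rule should follow the ban.

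Third, a reader might infer that no partner pregnancy could ever reach the sponsor or IRB. That is too strong. Section 17.2 counts a congenital anomaly as a serious outcome. Section 17.2.2 sends every serious event to the sponsor within 24 hours of awareness, whether or not it is thought drug-related, and requires prompt IRB reporting of unanticipated problems involving risks to subjects. These routes work only if the site hears of the case, and they do not reach an uneventful pregnancy.

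Fourth, the lack of any visible scheduled contact after Visit 5b might look like a gap specific to men. It is not: women have none either. The difference is that women are told to come forward and men are not.

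Fifth, the explanation about exposure through the parent might be read as including fathers. In context it follows a sentence about a pregnant female subject, so it neither creates a partner procedure nor proves an inconsistency.

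Finally, an instruction to men could sit in the consent form or on the Pregnancy form, neither of which is visible. That limits the reporting half of the point to the visible text. It would not correct criterion 13.

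**Conclusion.** The point holds as a minor misalignment plus a reporting gap in the visible text. For 59 to 62 days after the required methods end, men are barred from conception with no method specified. An uneventful partner pregnancy at any time from first dose to 3 months after last dose need not be notified or followed.

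The absolute risk is low: 9 to 12 days of active dosing, rapid clearance, negative genotoxicity studies and about 12 completers. The number of men is not stated and is taken as anywhere from 0 to 12. The conclusion rests on both rules counting from the same last dose and on the unseen consent and Pregnancy forms not supplying the missing duty. Nothing here threatens the trial's conclusions, and no sample size, endpoint or analysis is affected.

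**What to change.** 1. In criterion 13 (Study Summary and section 9.2) and in section 9.3.4, replace 30 days with 3 months as the end of required male birth control, to match the protocol's own ban. If the sponsor prefers to shorten the ban, it should state the reason.
2. Add to section 9.3.4 that men notify the site if a partner becomes pregnant at any time from first dose to 3 months after last dose.
3. Extend the recording, reporting and outcome follow-up in section 17.1.1 to those pregnancies, with the partner's consent.

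The cost is about two more months of contraception for men, a few sentences of text, and a partner consent form with IRB review. No visits or analyses change. Follow-up work arises only if a pregnancy occurs. Assuming 266 days from conception to birth, the latest case would run to 89 + 266 = 355 to 92 + 266 = 358 days after last dose, with contact about every three months as section 17.1.1 already suggests for subjects.

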10. STUDY PRODUCT AND RANDOMIZATION

10.1 Study Product and Treatment

The following products will be used in the study:

Test Product (Treatment A)

2 x 300 mg ADX-629 tablet taken PO bid for minimum 1 week (+3 days)

Placebo (Treatment B)

2 x 300 mg Placebo tablet taken PO bid for minimum 1 week (+3 days)

Dosing Instructions:

- [REDACTED]
- The subjects should take each dose at least 60 mins before food.
- There should be a gap of at least 4 hours between the two doses per day.
- The subjects should not take broken tablets; however minor tablet defects like chipping or scratching are acceptable.
- In case of an overdose, the subjects should hold the next dose and inform clinic immediately.
- In case of a missed dose, the subjects should take the dose when they remember only if their next scheduled dose is not within time frame of 4 hours. If the next scheduled dose is within time frame of 4 hours then subject should not take their missed dose and take the next dose at scheduled time.
- A minimum of two days of BID dosing during each treatment period are required before BAC/MCT.
- During Post-Treatment Periods 1 and 2 (Visits 4a, 4b, 5a, and 5b), in lieu of the morning dose, 600 mg of the treatments will be administered approximately one hour prior to MCT or BAC testing.

10.2 Randomization Sequence

At Visit 3, eligible subjects will be randomized to one of the two sequences shown below. The randomization will be generated in blocks of two with each sequence occurring once in each block.

The randomization schedule will be generated by using SAS® statistical software (Version: 9.4 or higher; SAS Institute Inc., USA). The randomization schedule will be generated by a biostatistician of [REDACTED] Limited.

The randomization schedule will be maintained under controlled access. The personnel involved in the dispensing of investigational products will be accountable for ensuring compliance to the

randomization schedule. The analytical staff concerned will not have access to the randomization schedule during the course of analysis.

Treatments will be administered according to a two-treatment, two-period, and two-sequence design.

	Period 1	Period 2
Sequence 1	A	B
Sequence 2	B	A

Number of subjects per sequence = 6

10.3 Masking and Unmasking

10.3.1 Masking

This is a double-masked clinical trial. Investigators, qualified site personnel (except pharmacy staff), and subjects will be masked to the investigational product administered. The Sponsor will also be masked to the IP administered until database lock. Only the pharmacy staff and Scientific Affairs staff involved with preparing the randomization will have access to the treatment under evaluation.

10.3.2 Emergency Unmasking

Emergency unmasking should only be performed when necessary to treat the subject. Most often, knowledge of the possible treatment assignments is sufficient to treat a clinical trial subject who presents with an emergency condition.

The investigator should make every effort to contact the Medical Monitor to discuss the subject's emergency and the need to unmask, prior to unmasking any subject.

In situations in which the investigator has tried but is unable to reach the Medical Monitor, best judgement on the part of the investigator should be used, based on the nature and urgency of the clinical situation, and may proceed with unmasking without having successfully reached and discussed the situation with the Medical Monitor. Once a subject's treatment assignment has been unmasked, the Medical Monitor should be notified within 24 hours of unmasking of the treatment, without revealing the treatment.

The emergency unmasking should be performed by the designated site personnel. The investigator must also indicate in source documents and in the CRF that the mask was broken and provide the date, time, and reason for breaking the mask.

Any AE or SAE associated with breaking the mask must be recorded and reported as specified in the protocol. The investigator has the responsibility to contact the Sponsor or designee within 24 hours of unmasking. In the event of a drug-related, serious, unexpected AE, the Sponsor's Pharmacovigilance Department or designee will be provided with the treatment assignment for the subject for regulatory reporting.

If treatment assignment is unmasked, the treatment will be discontinued immediately, and the subject will be discontinued from the clinical trial.

The mask may be broken in the case of a pregnancy should the subject desire this information.

11. STUDY CONDUCT

11.1 COVID-19 Screening

The following procedures will be performed as part of COVID-19 screening:

- Subjects will be pre-screened based upon a COVID-19 questionnaire at each clinic visit;
- Body temperature will be measured at each visit. This measurement may be in addition to other vitals taken at the visit;
- A nasal/nasopharyngeal/oropharyngeal swab will be collected for COVID-19 testing within 5 days prior to Visits 2a, 4a and 5a.
- Most recent COVID-19 test result (performed at Cliantha) will be reviewed prior to Visit 2a, 4a and 5a. Subject will be allowed to continue only if COVID-19 test result is negative.

Subject's further participation in the study will be based on the results of the COVID-19 test results and procedures.

11.2 Medical Screening: Visit 1 (Day - 28 to Day - 2)

The following activities will be completed at Visit 1:

- Verification of subject Identification (ID).
- Subjects will be asked to sign the Informed Consent Form.
- Demographic data including date of birth, age, race and ethnicity will be recorded.
- Medical, surgical, and social history and prior/concomitant medication use will be completed for each subject (see Section 12.2.2).
- An asthma control questionnaire will be completed.
- Vital signs (blood pressure, heart rate, respiratory rate, and oral temperature) will be measured (see Vital Signs Section 12.2.4).
- Height and weight will be measured and BMI will be calculated.
- A physical examination will be performed (see Physical Examination Section 12.2.3).
- Electrocardiogram (ECG) will be performed.
- A urine sample will be collected for urinalysis (see Clinical Laboratory Tests Section 12.2.1).
- Blood samples will be collected for clinical chemistry and complete blood count (CBC) with differential analysis (see Clinical Laboratory Tests Section 12.2.1).

- A urine pregnancy test will be performed (for all WOCBP). Subjects with a positive result will be excluded (see Clinical Laboratory Tests Section [12.2.1](#)).
- The subjects will be evaluated for study inclusion, exclusion, and restriction criteria.
- A skin prick test (SPT) will be performed to show positivity to cat or HDM allergen (≥ 3 mm wheal compared to negative control) (see Skin Prick Test Section [12.1.1](#)).
- Subjects will undergo spirometry to demonstrate baseline (pre-bronchodilator) FEV₁ of $\geq 80\%$ of the predicted value Post-bronchodilator FEV₁ will be measured within 15 ± 5 minutes following 400 μg (4 puffs) of salbutamol inhalation and post-bronchodilator reversibility will be recorded (see Spirometry Section [12.1.2](#)).
- Adverse events and concomitants medications will be recorded before subject leaves the site (see Adverse Event Query/Concomitant Medication Query Section [12.2.5](#)).

11.3 Pre-Treatment Period (3 consecutive days): Visit 2a, 2b and 2c (Day 1, 2 and 3)

- Subjects will return to the clinic for the pre-treatment period within approximately 4 weeks of Screening Visit.
- At all visits, the following procedures will be performed:
 - Verification of Subject ID.
 - The subjects will be evaluated for study inclusion, exclusion and restriction criteria.
 - Vital signs (blood pressure, heart rate, oral temperature and respiratory rate) will be measured (see Vital Signs Section [12.2.4](#)).
 - Adverse Event Query/Concomitant Medication Query: All subjects will be evaluated regarding their health status (see Adverse Event Query/Concomitant Medication Query Section [12.2.5](#)).

Visit 2a (Day 1):

- Asthma control questionnaire will be completed.
- Spirometry will be performed to ensure FEV₁ $\geq 80\%$ of the predicted value.
- Subjects will have a pre-BAC MCT performed as per the site standard procedures.
- Subjects will inhale normal saline and have a baseline FEV₁ established.
- Subjects will then be given subsequent doubling concentrations of Mch as per the site standard procedures (see Section [12.1.3](#)).
- FEV₁ will be measured at approximately 30 and 90 seconds following nebulization. If the FEV₁ drops $< 20\%$, the subject will be given the next highest concentration and spirometry repeated.
- Mch doses will continue to be administered sequentially (max concentration 4 mg/mL) until FEV₁ falls $\geq 20\%$ of the baseline. At such time, the test will be

terminated and subjects will be given 400 µg (4 puffs) of salbutamol, followed by a 15 ±5 minute waiting period prior to FEV₁ measurement.

- Subjects whose FEV₁ levels are not within 10% of their baseline will be given another dose of salbutamol as per Investigator's discretion and spirometry measurement repeated after 15±5 minutes. Mch PC₂₀ will then be calculated.
- All MCT will be performed at the same time of the day within a timeframe of ±1.5 hours throughout the entire study.
- Those who qualify will undergo a multi-skin prick sensitivity test with doubling concentrations of cat/ HDM allergen extracts. A positive control and a negative control will also be administered. The wheal diameter will be measured as per the site standard procedures (see Multi-skin prick sensitivity test Section 12.1.4).
- At Visit 2a, the subjects will be issued a diary (including Asthma Action Plan) to keep a daily log of any changes in their health or medication use (including rescue medication) in their diary while at home.
- Salbutamol inhaler with spacer (rescue medication) will be provided to the subject to take home at Visit 2a and rechecked at every Clinic Visit to ensure that the subjects have enough medication.
- The subjects will be given the option to be confined at the study site in order to facilitate early morning visit on the next day.

Visit 2b (Day 2):

- The next day after Visit 2a, subjects will undergo a BAC.
- Before the test can be performed, qualified personnel will explain the procedure and expected symptoms to the subjects.
- The allergen PC₂₀ to be administered will be determined based on the results from the MCT and allergy SPT titrations performed at Visit 2a (see Section 12.1.5).
- Following the calculation of the predicted allergen PC₂₀, post-saline FEV₁ i.e. baseline FEV₁ will be recorded (see Section 12.1.5).
- Subjects will then be given inhaled allergens as per the site's procedure until a 20% drop in FEV₁ is observed, or a maximum concentration of 5000 BAU/mL is given.
- When a drop in FEV₁ of 20% from baseline has finally been achieved the challenge will be terminated.
- In order to assess an EAR, FEV₁ will be measured at approximately 30, 60, 90, 120 and 180 minutes post allergen exposure. To assess LAR, FEV₁ will be measured every hour up to 7 hours post allergen challenge.
- At the end of the monitoring period, 4 puffs of bronchodilator will be administered to the subjects to restore FEV₁ to 90% of pretest FEV₁, if necessary. If FEV₁ does not return to normal levels, the Investigator/medical designee will assess the subject.

Following the test, sputum will be induced, collected, and processed (approximately 7 h post-BAC).

- At Visit 2b, the subjects' old diary (including Asthma Action Plan) will be collected and the subjects will be issued a new diary to keep a daily log of any changes in their health or medication use (including rescue medication) in their diary while at home.
- The subjects will be given the option to be confined at the study site in order to facilitate early morning visit on the next day.

Visit 2c (Day 3):

- The next day after Visit 2b, sputum induction and collection (approximately 24 h post-BAC) will be performed. Additionally, blood sample will be taken and sent to analytical lab for exploratory biomarkers (RASP and endotoxin-induced cytokine release). This will be considered as baseline value.
- At Visit 2c, the subjects' old diary will be collected and the subjects will be issued a new diary to keep a daily log of any changes in their health or medication use (including rescue medication) in their diary while at home. Subjects will also receive an asthma action plan to monitor asthma symptoms.
- Subjects will be asked to return to the clinic after approximately 2 weeks.

Note: Safety clinical laboratory tests will be repeated within 3 days prior to the first dose of study drug to ensure continued eligibility.

